flowcharts (Figure 1 & 2) for seeds and subsequent participants, respectively. Following wave 1 (seeds) (who will be recruited directly by study staff), potential participants will contact study staff by telephone. Women will send their recruitment coupon and official identification to verify age on an online platform, WhatsApp®. Eligibility criteria will be assessed telephonically, using a scripted eligibility screener preceded by verbal consent for eligibility screening. A copy of the study Informed Consent form will be sent to the participant and reviewed with her. The consenting procedure will be conducted telephonically and will be audio-recorded to document the participant's verbal consent. Potential participants will be told that the study includes (1) a pre- and post-intervention questionnaire; (2) GE: online activities prior to and after the group session and 1 online interactive-group workshop of 90 minutes; IA: being sent links to PrEP and contraceptive information and to a PrEP video; and (3) a 3-month follow-up **survey, with some participants selected for an interview**. After consenting, participants will complete a self-administered questionnaire.

**Conduct of workshops.** Both the GE and IA interventions will be conducted via WhatsApp, in English (and Zulu) by bi-lingual study staff. The GE workshop will begin with several assignments that are conducted asynchronously (i.e., participants are sent materials for an activity that they conduct on their own), followed by a 90-minute synchronous (i.e., in real time) interactive group session. To avoid contamination, PHAs will recruit only for the online condition they attended. In the GE condition a maximum of six attendees/workshop group is ideal; the minimum number of women needed to run a workshop will be four. Therefore, based on a sample of ~100, with ~50 in the GE condition, we expect to conduct 8-12 online GE workshop groups. In the IA condition, women will be sent the links for the online intervention materials as soon as they have completed the pre-intervention assessment. They can access and review these materials whenever they want. Women in both conditions will receive R200 R250 (~\$17.00) for completing the intervention and assessments. R50 will be given immediately upon

enrolling, so that women will be able to pay for mobile phone airtime to access the materials; the remainder will be given upon completion of the post-intervention assessment.

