Power Considerations. The primary goal for this pilot work is to collect preliminary data regarding feasibility, acceptability and target outcomes for the proposed intervention. In line with guidelines from PA-17-166: *Formative and Pilot Intervention Research for Prevention and Treatment*, which caution against using pilot studies (where the sample size is of necessity small) to obtain an estimate of an effect size, we will use these pilot data to rule out unusually large or small true effects through standard 95% confidence interval procedures. We will confirm extrinsic effect sizes are contained within our confidence intervals from the pilot. We will examine the distribution of each variable, and calculate summary statistics by intervention condition. We will estimate key intervention parameters with sample means and proportions together with two-sided 95% confidence intervals, and test the primary null hypotheses at the traditional two-sided level  $\alpha=.05$  (simulation of the subsequent RCT). For planning the RCT, we will also consider one-sided 90% confidence limits for mission-critical *design parameters* such as standard deviations and reference group endpoint rates and proportions in the conservative direction. This is because we intend to plan sample size for the RCT so that power will be “excellent” (at least 80% power) for the clinically relevant effect size to be specified. This strategy will make proper allowance for the limited sample size of the pilot study with its consequent uncertainties, and still yield appropriate sample sizes for the RCT. “Mission-critical” parameters include proportions for dichotomous endpoints (uptake of PrEP clinical assessment, uptake of PrEP yes/no); means and standard deviations for continuous potential mediators of outcome (e.g. gender barriers, PrEP-stigma). Large sample sizes are not required to locate these parameters approximately, but adequately, for planning the subsequent trial, whereas testing the study hypothesis in the pilot

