will generally not have sufficient statistical power. Estimation of mission-critical design parameters with point and confidence interval estimates will be considered highly important; continuous outcome measures make it feasible to detect promising effect effects even in small samples. For the continuous measures, means and standard deviations (sd) will be estimated. For approximately normally distributed variables, an upper one-sided 90% confidence limit for the sd,  $\sigma_u$ , will be constructed from  $\sigma_u = s \chi^2_{v,10}^{1/2}$ , where s is the sample sd and  $\chi^2_{v,10}$  is the upper 10th percentile of the chi-squared distribution with v degrees of freedom. For approximately log-normally distributed variables, a logarithmic transformation will be applied to achieve approximate symmetry and normality. For the dichotomous variables (such as the primary and secondary outcomes, or the PDR performance criteria), exact binomial methods will be employed for the CIs for proportions. As an example, the width of the exact 95% confidence interval around a point estimate of 40% (e.g., percent women who score high-risk) would be 30%-50% with 100 participants.

While testing the primary null hypothesis is not the primary goal for this pilot study, if we assume the proportion of women who undergo PrEP clinical assessment in the information-only group ranges from 20% to 50%, with total sample size of 100 participants we are still able to declare a difference of 33 to 36 percentage points as statistically significant at 0.05 level with power of 80% if the within recruitment chain and within intervention-delivery group correlation coefficient is no greater than 0.1. As an illustration of how this can be used for planning the large randomized trial, suppose in this pilot study, proportion of participants take PrEP risk screening is 85% and 50% for Gender-Enhanced workshop and Information-Only Workshop respectively while the minimally clinically relevant improvement, on extrinsic grounds, is an improvement of 15 percentage points. Then, N=240 per group would be required in the RCT. The above plan will allow us to assess feasibility and acceptability, estimate factors influencing intervention parameters, and examine the range of possible effect sizes for our primary outcome. Therefore, the information collected from this pilot study should put us in an excellent position to conduct a future full-scale RCT.

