## Data Analysis

Workshops: Compare women randomized to the virtual group-interactive workshop with those randomized to individually-accessed links to a PrEP promotional video and PrEP information on the **primary outcome of having an individual discussion with the study nurse about the possibility of taking up PrEP; undergoing HIV self-testing guided by the study nurse (either in-person at the GHRU office or via telehealth visit) (secondary outcome); if eligible for PrEP, initiating PrEP (secondary outcome)**, and, for all women, changes in hypothesized mediators (information, risk perception, gender barriers, outcome beliefs, PrEP-stigma, peer norms) post-intervention and at 3-month follow-up.)

To compare the **primary and secondary outcomes** across the two workshop conditions, we will use generalized linear models (GLM) with a logit link function and the method of generalized estimating equations (GEE) to account for the effect of clustering within recruitment chain. The logit link function is appropriate because the primary and secondary outcomes are dichotomous and characterized as yes/no if achieved at any time over the course of the study by the time of the 3-month follow-up interview. Intervention condition (Gender-Enhanced or Individual Access) is the primary predictor. Although the original data analysis plan also specified accounting for clustering by workshop group attended, we will not account for clustering by workshop group because women in the IA condition received the intervention as individuals rather than as groups.

We will adjust for any substantial baseline differences by condition on age. We will also adjust for any substantial differences by other demographic and behavioral characteristics, such as education level, whether attending school, has a primary partner, sexual risk behaviors (to be defined), relationship power, reported intimate partner violence if these factors differ substantially by condition at baseline and are also associated with the outcome (i.e., meet the conditions of confounding).

To assess if being a PHA, i.e., talking to other women about HIV prevention serves as an additional intervention dose, a secondary analysis will include a variable for whether the woman served as a PHA and recruited other workshop attendees (yes/no).

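### The SAP's upper 90% confidence limit for a standard deviation names the wrong chi-squared tail: a minor definition error that only touches planning of a later trial

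*SAP*

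**What the plan says.** The rule is in SAP section 3.3.9.3, Power Considerations, in the part headed as coming from the original proposal. For approximately normal continuous measures the SAP will construct "an upper one-sided 90% confidence limit for the sd" from the sample SD, s, and the square root of a chi-squared quantile with subscript v,10. It then defines the quantile in words: it "is the upper 10 th percentile of the chi-squared distribution with v degrees of freedom".

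The purpose is given in the same section. For planning the later randomized trial, the team will also look at one-sided 90% limits for design parameters "such as standard deviations and reference group endpoint rates and proportions in the conservative direction", so that the later trial has at least 80% power. The parameters listed include "means and standard deviations for continuous potential mediators of outcome".

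No value of v is given and no limit is worked out. The SAP plans to "calculate summary statistics by intervention condition" and assumes 100 participants in total. The Protocol, under Conduct of workshops, plans the groups "based on a sample of ~100, with ~50 in the GE condition".

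**The concern.** A large SD is what makes a trial too small, so a conservative planning value for an SD must lie above the sample value. The quantity v·s²/σ² follows a chi-squared distribution on v degrees of freedom, and σ is large relative to s when that quantity is small. The upper limit for σ therefore comes from dividing by the lower 10th percentile. The SAP names the opposite tail.

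If the usual form of the limit was intended, following the stated definition would give a planning SD below s, which is the reverse of the conservative direction that the SAP asks for. What is at stake is the reliability of a planning value for a continuous mediator in a later trial, and nothing in the pilot comparison itself.

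**Working it through.** **Inputs.** Confidence level 90%, one-sided, upper (SAP, Power Considerations). Quantile: the point with 10% of the distribution above it (same sentence). Degrees of freedom: not stated. I assume v = 49 for one arm of about 50, and v = 98 for two arms pooled (100 − 2). The chi-squared result also assumes independent, approximately normal observations. The SAP gives no numerical limit, so there is no figure of its own to reproduce; what can be checked is whether the stated 90% is met.

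**Coverage of a limit f·s.** P(σ ≤ f·s) = P(χ²_v ≥ v/f²).

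**Chi-squared points.** v = 49: lower 10% point 36.82, upper 10% point 62.04. v = 98: 80.54 and 116.32.

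**Forms that the sentence could mean, each with the stated (upper) tail, at v = 49.**

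- (a) Usual form, s·√(v/χ²): √(49/62.04) = 0.889, so 0.889s. Coverage is P(χ² ≥ 62.04) = 10%. This is a lower 90% limit.
- (b) Inverted form, s·√(χ²/v): √(62.04/49) = 1.125, so 1.125s. Coverage is P(χ² ≥ 49²/62.04 = 38.70) = 85%.
- (c) As it reads, with no v, s·√χ²: √62.04 = 7.88, so 7.88s. Coverage is P(χ² ≥ 49/62.04 = 0.79), about 100%.
- Correct: s·√(v/χ² lower 10%): √(49/36.82) = 1.154, so 1.154s. Coverage is P(χ² ≥ 36.82) = 90%.

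**The same at v = 98.** (a) √(98/116.32) = 0.918s, 10%. (b) √(116.32/98) = 1.089s, 87%. (c) √116.32 = 10.79s, about 100%. Correct: √(98/80.54) = 1.103s, 90%.

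**What each would do to a sample size.** The size needed to compare two means is proportional to the square of the planning SD. Relative to the correct limit at v = 49, form (a) gives 36.82/62.04 = 0.593 of the number and form (b) gives (1.125/1.154)², about 0.95. At v = 98, form (a) gives 80.54/116.32 = 0.692 and form (b) about 0.975. Form (c) gives a value too large to use.

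**Changing the tail alone is not always enough.** If the missing v is a real omission, putting the lower point into the formula as it reads gives √36.82 = 6.07, so 6.07s at v = 49. Formula and definition have to be corrected together.

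**The case against.** **It may be a one-word slip.** If the subscript v,10 was meant as the ordinary 10th percentile, with 10% of the distribution below it, then the usual form (a) is exactly right and only the word for the tail is wrong. The missing v may also be no more than a conversion loss, and I do not count it as an error. This stands as far as size is concerned. It does not rescue the definition: the tail is written out in prose, and an analyst who codes it as defined will not get a 90% limit under any of the three forms. Forms (a) and (c) would probably be noticed, since one falls below s and the other is about eight times s. Form (b) gives a plausible number and could pass unseen.

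**The rule may no longer apply.** It sits in carried-over text, and the current Data Analysis section deals with the mediators by GEE models without mentioning an SD limit. That section does announce one departure ("Although the original data analysis plan also specified accounting for clustering by workshop group attended"), and a reader might infer that everything not withdrawn still holds. The documents do not support that inference. The current text also drops items without comment: 3-month PrEP retention as a secondary outcome, and self-efficacy and attitudes from the mediator lists. Silence therefore shows neither that the rule was kept nor that it was dropped.

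**The consequence is remote.** The SAP says only that these limits will be considered in planning. Its one worked example for a later trial uses proportions, and the primary and secondary outcomes are dichotomous. This objection stands, and it keeps the point minor.

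**Conclusion.** The definition is wrong as written, and the error is minor. With the stated tail no reading of the formula gives a 90% upper limit: coverage at v = 49 is 10%, 85% or about 100%, against a correct limit of 1.154s (1.103s at v = 98). I am confident about the tail. The size and direction of the error are not settled, because the intended formula cannot be read and v is not stated.

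A reader might infer from form (a) that the later trial would be about 41% too small (1 − 0.593). The documents do not support this. It takes one of three possible forms as the intended one, an assumed v, a rule that is still in force, and a later trial sized on a mediator SD, which no section describes. The primary and secondary outcomes, the between-arm tests and the size of the pilot are unaffected.

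**What to change.** Replace the sentence with: σ_u = s·√(v/χ²_{v,0.10}), where χ²_{v,0.10} is the lower 10th percentile of the chi-squared distribution with v degrees of freedom, that is, the point with 10% of the distribution below it. State whether v is per arm or pooled. Add the check that σ_u must exceed s (1.154s at v = 49, 1.103s at v = 98). Say in the current Data Analysis text whether these planning limits are still to be computed; if not, mark the carried-over rule as withdrawn.

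The cost is one line of SAP wording plus a statement of status. Data collection, the outcome analyses and the pilot's size do not change.

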their own time as well as a “real-time” “live” interactive session) or to an Individual Access (IA) condition in which women are given access to a PrEP video and to websites that provide information on PrEP and on contraception options. The primary outcome is having an individual conversation with the study nurse about the possibility of taking up PrEP; secondary outcomes are undergoing HIV-testing and counseling and, if PrEP-eligible, taking up PrEP; and, for all women, *hypothesized mediators* (risk perception, gender barriers, peer norms, self-efficacy, outcome expectancies, PrEP-stigma, attitudes, information) post-intervention and at 3-months. For *Peer-driven recruitment (PDR)* AGYW randomized to either condition will be invited to become *Peer Health Advocates (PHAs)*, who are incentivized to talk to social network members and refer up to three to the workshop type the PHA attended. We will evaluate acceptability and feasibility of PDR by assessing whether the method can be self-sustaining (i.e., on average >50% attendees become PHAs and >2 recruits/PHA attend a workshop); and whether it reaches high-risk women, and women who would not be captured by other methods of recruitment (percent who score high on a new HIV risk tool; percent who never tested or attended family planning). If promising, these approaches will be further tested in a larger study.

Additionally, women who participated in Phase 1 FGs (N = 46) of this study will be invited to participate in a sub-study entitled Sexual and Reproductive Health and Rights of Young Women under the COVID-19 Epidemic (COVID and SRHR). The goal of the sub-study is to understand how the Coronavirus epidemic and related lock-down regulations are affecting young women’s sexual and reproductive health and rights (SRHR) needs and ability to access sexual and reproductive health commodities and services over time (before, during different levels of and after lock-down). Participating women will complete three to four telephone interviews (depending on how long the lock-down lasts) over a one-year period. The interviews will employ mixed methods (quantitative, qualitative and photo-voice). Data collected as part of the sub-study will be combined with the quantitative descriptive data on demographic and sexual and reproductive health characteristics obtained from participating women just prior to the beginning of each FG.

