In total, we expect that **98** ~~100~~ women will attend and complete the intervention and assessment activities. To balance recruitment chain size, PHAs will be allowed up to 3 recruitees. PHAs *will not* assess eligibility for workshop attendance, but they will be able to inform potential recruitees of age eligibility, that interactive groups will be audio-recorded, and that the intervention activities are for women *who have had sex*. PHAs will receive R100 (approximately

\$7.69) for each recruitee who is eligible and participates in the activities; they will be told that they will not be paid unless their recruitee is eligible for and completes the activities. To reduce the possibility of coaching, PHAs will be told that staff will confirm criteria; proof of age will be required, and the assessment will ask several questions about sexual activity that may reveal inconsistencies if the recruit was never sexually active. To reduce the possibility of coercion, in the eligibility screener we will ask recruitees how long they have known the PHA who recruited them and if they felt coerced in any way to attend. Any PHA found to be engaging in such behavior will be informed that she may no longer recruit and that she will not get paid for any recruitees who report her as their recruiter.

Procedures for Eligibility screening, informed consent, and study enrollment. Procedures are shown in the

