We also will ascertain women's use of PrEP and other prevention strategies through the follow-up interview (self-report).

Acceptability of the workshops will be assessed with items such as *the workshop was fun, boring, too long, too short; I didn't understand most of what was going on; I would recommend the workshop to a friend*. Feasibility of the workshops will be assessed using tracking data for (number attended, number who agreed to be PHAs) and facilitators' summary reports documenting any challenges.

**Acceptability and feasibility of Peer Driven Recruitment.** Data for indicators of acceptance and successful contacts will be obtained by tracking the number of women who agree to be PHAs and take referral coupons and, for each PHA, the number of recruits who meet eligibility criteria and attend the workshop. **Reach** will be assessed by proportion of recruits who (1) score *high* on the risk tool and (2) have never been tested and never attended a family planning clinic (an indicator of reach into networks unconnected to care). The pre- and post-workshop assessments are expected to take 15-20 minutes; the follow-up assessment is expected to take 20 to 40 minutes, depending on use of PrEP.

**In-depth Brief telephone** interviews will cover topics related to outcomes of the interventions, any behavior changes including PrEP uptake that were adopted, and their experiences in successfully recruiting (or not) other women to the intervention.

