**Aim 3b.** Peer-driven recruitment: 1) Assess acceptability and feasibility of PDR using pre-specified performance (process) criteria for acceptance and recruitment (on average  $\geq 50\%$  of attendees become PHAs and  $\geq 2$  recruits/PHA attend a workshop); and 2) Evaluate reach of PDR (percent who score high on a new HIV risk tool (10); percent who never tested and never attended family planning. We will estimate these simple proportions from the tracking data and from the pre-workshop assessments.

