3. **Pilot (revised):** To evaluate acceptability, feasibility, and outcomes of the intervention components:
  - a. Intervention: Compare women randomized to the virtual group-interactive workshop with those randomized to individually-accessed links to a PrEP promotional video and PrEP information on the ***primary outcome of having an individual discussion with the study nurse about the possibility of taking up PrEP; undergoing HIV self-testing guided by the study nurse (either in-person at the GHRU office or via telehealth visit) (secondary outcome); if eligible for PrEP, initiating PrEP (secondary outcome),*** and, for all women, changes in hypothesized mediators (information, risk perception, gender barriers, outcome beliefs, PrEP-stigma, peer norms) post-intervention and at 3-month follow-up.
  - b. Peer-driven recruitment: 1) Assess ***acceptability and feasibility*** of peer-driven recruitment (PDR) using pre-specified performance criteria for acceptance and recruitment (on average  $\geq 50\%$  attendees agree to recruit other women (i.e., become Peer Health Advocates [PHAs] and  $\geq 2$  recruits/PHA enroll in the study); and 2) evaluate ***reach*** of PDR (percent who score high on HIV risk assessment; percent who never tested or never attended family planning).

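### The recruits-per-PHA criterion is a mean of a 0–3 count, but the SAP classes it as dichotomous and assigns it an exact binomial interval

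*SAP*

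**What the plan says.** The Protocol's Lay Summary defines self-sustaining peer recruitment as "on average >50% attendees become PHAs and >2 recruits/PHA attend a workshop". Its Specific Aims and the SAP write both thresholds as at least rather than more than. The averaging phrase governs both parts.

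For the second part, the Protocol's Assessment Instruments section (acceptability and feasibility of Peer Driven Recruitment) records "for each PHA, the number of recruits who meet eligibility criteria and attend the workshop". The pilot recruitment text sets the ceiling: "PHAs will be allowed up to 3 recruitees". The data are therefore one count per PHA, taking the values 0, 1, 2 or 3.

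On analysis, the Aim 3b paragraph of SAP 3.3.9.3 says of the criteria and the reach measures: "We will estimate these simple proportions from the tracking data and from the pre-workshop assessments". Power Considerations then assigns the interval method: "For the dichotomous variables (such as the primary and secondary outcomes, or the PDR performance criteria), exact binomial methods will be employed".

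The definition of a recruit also moves within the SAP. Aim 3b counts "recruits/PHA attend a workshop", while the revised aim under the December 2020 heading counts "recruits/PHA enroll in the study". The later Data Analysis section contains no peer-recruitment analysis, so the two paragraphs of 3.3.9.3 are the only plan for these criteria.

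**The concern.** The two criteria are different kinds of quantity. The share of attendees who become PHAs is a proportion, and an exact binomial interval is a natural choice for it. Recruits per PHA is a mean, and its uncertainty depends on how much the counts vary between PHAs. A binomial interval contains no term for that variation.

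The mean is also what the plan's reasoning needs. The Protocol's recruitment cycle is 28 attendees × 50% × 2 recruits = 28 new attendees. Only the average number of recruits enters that product; the share of PHAs who reach 2 does not.

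At stake is how one of the two self-sustainability criteria is reported. The planned yield is close to the threshold, so the interval's width would affect how firmly a reader takes the criterion to be met or missed.

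**Working it through.** **The SAP's own figure.** Exact (Clopper–Pearson) limits for x out of n are the 0.025 quantile of Beta(x, n−x+1) and the 0.975 quantile of Beta(x+1, n−x). For 40 of 100 they are 30.3% and 50.3%, which matches the SAP's 30%–50%. That example concerns the percentage scoring high-risk, which is a true proportion, and it is correct.

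**Inputs for criterion 2.** From the Protocol's planned waves: 16 seeds bring 28 recruits, then 14 PHAs bring 28, then 14 bring 28. Recruiting PHAs: 16 + 14 + 14 = 44. Recruits: 3 × 28 = 84. Planned mean: 84/44 = 1.91 overall and 28/16 = 1.75 for the seeds. The count distribution is not given, so a range is assumed below, each case with a mean of exactly 2.

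**Reading (a): each PHA scored as 2 or more, yes/no.**
- A 60% share fits a mean of 0.4×0 + 0.6×2 = 1.2 at the lowest and 0.4×1 + 0.6×3 = 2.2 at the highest. The first fails the criterion and the second passes.
- Conversely, let a share q have 2 or more recruits. The largest possible mean is 3q + (1−q) = 1 + 2q, so a mean of 2 needs q of at least 50%. It can be as high as 100%, when every PHA recruits exactly 2.
- With 44 PHAs, those two extremes give exact intervals of 34.6%–65.4% (22 of 44) and 92.0%–100% (44 of 44). They do not overlap, yet both samples have a mean of exactly 2.

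**Reading (b): three places per PHA as independent trials.** At a mean of 2 there are 88 recruits in 132 places. The exact limits multiplied by 3 are 1.74 to 2.24. This treats the per-PHA variance as 3 × (2/3) × (1/3) = 0.67. The largest variance possible for a 0–3 count with mean 2 is 2 × (3−2) = 2.0.

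The t-interval is 2 ± 2.017 × √(variance/44). Coverage is the share of 20,000 simulated sets of 44 independent PHAs in which the slot interval contained 2.

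| Assumed % of PHAs with 0/1/2/3 recruits | Variance | t-interval for the mean | Coverage of the slot interval |
|---|---|---|---|
| 0/10/80/10 | 0.20 | 1.86–2.14 | over 99.9% |
| Binomial(3, 2/3) | 0.67 | 1.75–2.25 | 96.0% |
| Equal thirds at 1, 2, 3 | 0.67 | 1.75–2.25 | 95.9% |
| 20/10/20/50 | 1.40 | 1.64–2.36 | 83.9% |
| One third at 0, two thirds at 3 | 2.00 (maximum) | 1.57–2.43 | 73.0% |

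At the maximum variance the t-interval is 0.86 wide against 0.50 for the slot interval, about 1.7 times.

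**Denominator.** All participants are invited to become PHAs, and the wave table has a row for Wave 4 attendees who do so. If half of the 28 Wave 4 attendees agreed (14, applying the plan's 50%) and had no later wave, including them would give 84/(44+14) = 84/58 = 1.45 instead of 1.91.

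**Numerator.** The Protocol allows up to 120 enrolled for about 100 completers. If all 20 extra women were recruits who enrolled but did not take part, the two definitions would differ by 20/44 = 0.45 recruits per PHA. That is the upper end of an assumption; the documents do not split the 20.

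**The case against.** The strongest reply is that this is loose wording that any analyst would repair. Power Considerations also promises "sample means and proportions together with two-sided 95% confidence intervals", which would cover a mean per PHA. The exact method is described as being for proportions, so an analyst holding per-PHA counts could apply the general sentence to criterion 2 and the binomial one to criterion 1. This shows that the right analysis is within the plan's reach, but it does not remove the conflict. The later sentence names the peer-recruitment criteria, in the plural, as dichotomous, and Aim 3b calls the quantities proportions. A specific assignment prevails over a general one.

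Three further objections stand and limit the point:

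- A reader might infer that the planned interval is bound to be too narrow. The documents do not support that. Reading (b) appears nowhere in them; it is one way of making the binomial instruction work. It under-covers only if the count variance exceeds 0.67, and at or below that it is adequate or conservative. The 73% figure is the worst case.
- A reader might infer that the SAP prints a wrong interval for this criterion. It prints none for either peer-recruitment criterion.
- A reader might infer that the interval decides whether the criterion is met. No section says that a confidence limit must reach 2. The point estimate, recruits divided by PHAs, is unaffected by the interval method.

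The affected text also sits under the heading for the original proposal. Nothing later replaces it, so it remains the plan.

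**Conclusion.** The misclassification is real: a mean of a 0–3 count is listed as dichotomous and given an interval that does not apply to it. Reading (a) changes the statistic. Reading (b) may give an interval that is too narrow or too wide, with coverage from 73% to over 99.9% across the assumed distributions; which way it errs is unknown because the documents give no distribution. These figures assume 44 PHAs, a true mean of 2 and independence between PHAs.

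The effect is confined to the reporting of one feasibility criterion. The primary outcome, the first peer-recruitment criterion and the SAP's 30%–50% example are not touched. Recruits per PHA is also not among the mission-critical parameters that the SAP lists for planning the larger trial. This is a minor-to-moderate correction, worth making because it is cheap and because the definitions of recruit and of the PHA denominator need settling in any case.

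**What to change.** In SAP 3.3.9.3 (Aim 3b and Power Considerations):

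1. Keep exact binomial intervals for yes/no items, including the share of attendees who become PHAs.
2. Define criterion 2 as the mean number of recruits per PHA. Give a 95% interval from the between-PHA variation, by t or bootstrap, allowing for recruitment chain. If chains are resampled, note that the plan starts from 16 seeds, so there are few independent units unless new seeds are added.
3. Choose one definition of recruit, reconciling attendance in Aim 3b with enrolment in the December 2020 revision.
4. Restrict the denominator to PHAs who had a subsequent wave in which to recruit.
5. Report the mean and interval beside the threshold of 2, with the numbers of PHAs at 0, 1, 2 and 3. The share with 2 or more can be shown as description only.

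The cost is about one sentence of SAP text, two definitions and minor programming on tracking data that are already planned. The interval may come out wider if recruitment is concentrated in some PHAs.
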